7. STUDY ASSESSMENTS

7.1. Efficacy Assessments

7.1.1. Urinary Protein:Creatinine and Albumin:Creatinine

Proteinuria will be assessed by measuring the protein, albumin, and creatinine concentrations on first morning urinary samples, and calculating the urinary protein:creatinine ratio and urinary albumin:creatinine ratio. Results will be expressed as mg protein/g creatinine or mg albumin/g creatinine. This will be done by the central laboratory.

7.1.2. Estimated Glomerular Filtration Rate

Estimated glomerular filtration rate (eGFR) will be calculated at the study visits indicated in the [Time and Events Table](#) using the following MDRD equation:

$$\text{eGFR (mL/min/1.73 m}^2\text{)} = 175 \times (\text{serum creatinine in mg/dL})^{-1.154} \times (\text{Age})^{-0.203} \times (0.742 \text{ if female}) \times (1.212 \text{ if African-American/Black})$$

Cystatin C measurements may be used to calculate eGFR using the following equation:

$$\text{eGFR}_{\text{cys}} \text{ (mL/min/1.73 m}^2\text{)} = 127.7 \times (\text{cystatin C in mg/L})^{-1.17} \times (\text{Age})^{-0.13} \times (0.91 \text{ if female}) \times (1.06 \text{ if African-American/Black})$$

7.1.3. Other Urinary Assessments

First morning urine samples will be analyzed for hematuria, when appropriate at the study visits indicated in the [Time and Events Table](#). Microscopic review is triggered if a urinary dipstick test is positive for WBC, RBC, nitrite, or protein. When microscopy is performed, hematuria will be categorized as follows: None, Occasional (Occ), 1 - 2, 3 - 5, 6 - 9, 10 - 15, 16 - 29, 30 - 49, 50 - 75, and >75 RBCs per high power field. For the purpose of analyzing the change from baseline in urinary RBCs, the following values will be assigned for each category:

$$\text{None} = 0.1, \text{Occ} = 0.5, 1 - 2 = 1, 3 - 5 = 3, 6 - 9 = 6, 10 - 15 = 10, 16 - 29 = 16, 30 - 49 = 30, 50 - 75 = 50, >75 = 75.$$

Urine MCP-1 and EGF levels will also be measured by the central laboratory in urine samples by specific ELISA at the study visits indicated in the [Time and Events Table](#). Urine creatinine will be measured in the same urine samples. MCP-1 and EGF levels will be standardized to urine creatinine and expressed as pg MCP-1/mg creatinine and pg EGF/mg creatinine. Urinary EGF:MCP-1 ratios will be calculated from the creatinine-corrected values.

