7.2. Other Efficacy Endpoints

1. Proportion of subjects achieving renal response, defined as an improvement in proteinuria based on a decrease from baseline to Day 85 in proteinuria to a level <300 mg/g creatinine and maintaining estimated glomerular filtration rate (eGFR) within 15% of baseline
2. Proportion of subjects achieving a partial renal response, defined as an improvement in proteinuria based on a decrease from baseline to Day 85 in proteinuria to a level <1 g/g creatinine and maintaining eGFR within 15% of baseline
3. Change in slope from the run-in period to the treatment period for
 - a. urinary ACR,
 - b. eGFR,
 - c. urinary MCP-1:creatinine ratio,
 - d. urinary EGF:MCP-1 ratio, and
 - e. urinary microscopic RBC counts
4. Percent change from baseline to Day 85 in
 - a. urinary PCR and
 - b. urinary ACR
5. Change from baseline (CFB) to Day 85 in eGFR
6. In patients with hematuria at baseline, the percent change from baseline in urinary RBC count
7. Percent change from baseline to Day 85 in urinary MCP-1:creatinine ratio
8. Percent change from baseline to Day 85 in serum IgA:plasma C3 ratio
9. Percent change from baseline to Day 85 in urinary EGF:MCP-1 ratio
10. Percent change from baseline in plasma and urinary biomarkers, e.g., C3a, C5a, properdin, and sC5b-9; if performed, results from these analyses will be presented in a separate report

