9.3. Data Presentation

The following rules describe reporting conventions for the study.

- Report output will be provided as Rich Text Format (RTF) or Portable Document Format (PDF) documents generated using SAS.
- Font – Courier New or SAS font with minimum of 9 point font size for tables and 7 point for listings.
- Margins – Minimum of 3/4" bound edge margin and 3/8" other margins on 8.5"x11" paper as per the FDA guidance for e-submission.
- Continuous data will be summarized using n (number of subjects with non-missing observations), mean, median, standard deviation (STD), minimum value, and maximum value. Geometric means and geometric mean ratios (Visit:Baseline) will also be provided for urinary PCR, ACR, RBC count, MCP-1:creatinine, EGF:MCP-1 ratio, EGF:MCP-1 ratio, and serum IgA:plasma C3 ratio. Confidence intervals will also be provided for efficacy parameters.

- Categorical data will be summarized using the frequency count and percentage (n, %) of subjects in each category. Confidence interval for the percentage will be calculated for the efficacy variables.
- Number of subjects with non-missing values or number of subjects with missing values (eg, Not Done) will be presented, where appropriate. Subjects with missing values will not contribute to the denominator of percentage calculations.
- Counts of zero in any category will be presented without percentage.
- Precision of summary statistics:
 - Sample size (n, N) and number of missing responses (if displayed) – Integer.
 - Mean, confidence interval – One additional decimal place than reported/collected.
 - Standard deviation – Two additional decimal places than reported/collected.
 - Median, other percentile, minimum, maximum – Same number of decimal places as reported/collected.
 - Ratios – two decimal places.
 - Percentages – one decimal place generally, or two decimal places for <0.1%.
- Data listings will include pertinent subject information, eg, treatment, age/gender/race, study day. These will be sorted in the order of subject ID, assessment date/time and assessment (in the order collected on CRF, unless specified otherwise).
- Dates will be presented in the ISO-8601 format YYYY-MM-DD. Times will be displayed in 24-hour clock format.
- Numbering for tables, figures and listings will follow ICH E3 Guidelines.

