10.2.10. Missing, Unused, and Spurious Data

No imputation will be carried out for missing data points.

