10.7.5. Percent change from baseline to Day 85 in

- a. urinary PCR and
- b. urinary ACR

Urinary PCR and ACR will be summarized with geometric mean, median, minimum, and maximum at each visit. Percent change from baseline will be based on the geometric mean ratios of Visit:Baseline. The 95% confidence interval for the geometric mean ratios will be presented.

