10.7.6. Change from baseline to Day 85 in eGFR

Estimated GFR and its change from baseline will be summarized with arithmetic mean, standard deviation, SEM, median, minimum, and maximum at each visit. The 95% confidence interval for the change will be presented.

10.7.7. In patients with hematuria at baseline, the percent change from baseline in urinary RBC count

For the purpose of analysis, urinary RBC count will be recoded as follows. None = 0.1, Occ = 0.5, 1 - 2 = 1, 3 - 5 = 3, 6 - 9 = 6, 10 - 15 = 10, 16 - 29 = 16, 30 - 49 = 30, 50 - 75 = 50, >75 = 75.

The method of summary described in Section 10.6.5 applies here.

- 10.7.8. Percent change from baseline to Day 85 in urinary MCP-1:creatinine ratio;
Percent change from baseline to Day 85 in serum IgA:plasma C3 ratio ;
Percent change from baseline to Day 85 in urinary EGF:MCP-1 ratio

The method of summary described in Section 10.6.5 applies here.

- 10.7.9. Shift in Urinary PCR, ACR, and hematuria

Shift tables will be created for urinary parameters, such as urinary PCR, ACR, and red blood cells, from baseline to each visit. The categories of interest are <300 mg/g, 301-1000 mg/g, \geq 1000 mg/g for PCR and ACR, and \leq 5 RBCs/hpf, >5 to <30 RBCs/hpf, and \geq 30 RBCs/hpf for urinary RBC count.

- 10.7.10. Percent change from baseline in plasma and urinary biomarkers, e.g., C3a, C5a, properdin, and sC5b-9

If conducted, the results will be presented in a separate report.

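### A urine sample with a fully negative dipstick may have no RBC count: Protocol 7.1.3 and the visit schedule disagree on when microscopy is done, and the SAP has no code for an untriggered sample

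*Protocol*

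**What the plan says.** Protocol 7.1.3 (Other Urinary Assessments) has first morning samples analysed for hematuria where appropriate, and sets the condition: "Microscopic review is triggered if a urinary dipstick test is positive for WBC, RBC, nitrite, or protein". The ten RBC categories, from None to more than 75 per high power field, are introduced there as applying when microscopy is performed.

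The schedules set no such condition. The Time and Events Table and the SAP schedule list a microscopic RBC count at the run-in visits and on Days 1, 8, 15, 29, 57, 85, 113, 141 and 169. The visit lists in Protocol section 6 (for example 6.10, Day 85) do the same.

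SAP 10.7.7 turns the categories into numbers, beginning "None = 0.1, Occ = 0.5, 1 - 2 = 1, 3 - 5 = 3". It has no entry for a sample that did not go to microscopy. SAP 10.2.10 adds: "No imputation will be carried out for missing data points". SAP 9.3 adds: "Subjects with missing values will not contribute to the denominator of percentage calculations".

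Three planned outputs use the RBC count:
- the endpoint in SAP 7.2, "In patients with hematuria at baseline, the percent change from baseline in urinary RBC count";
- the RBC slope in SAP 10.7.4;
- the RBC shift table in SAP 10.7.9.

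For the percent change, 10.7.7 refers to a Section 10.6.5 that does not exist. I read it as 10.7.5, which says: "Percent change from baseline will be based on the geometric mean ratios of Visit:Baseline". SAP 9.3 supports this reading, because it names RBC count among the variables given geometric mean ratios.

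**The concern.** Under the 7.1.3 trigger, whether a count exists depends on the result. A sample with neither blood nor protein, and no WBC or nitrite, is the best outcome the hematuria scale could record, and it is the one sample type that yields no value. The loss therefore depends on the outcome and makes the fall in RBC count look smaller than it was.

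Change in hematuria is a secondary objective. The study enrolls up to about 20 subjects, and the percent change is computed only in those with hematuria at baseline, so one or two missing values can move the estimate. In the shift table, a cleared subject would not appear in the lowest category (5 or fewer RBCs/hpf) at that visit.

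**Working it through.** No figure in the plan depends on this rule, so there is nothing to reproduce. The check is a trace of the rule followed by an illustration.

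**Trace of one sample negative for WBC, RBC, nitrite and protein**
1. Protocol 7.1.3: microscopy is not triggered, and the categories (including None) do not apply.
2. SAP 10.7.7: no numeric code is given for this case.
3. SAP 10.2.10: the gap is not filled.
4. Result: no RBC value at that visit. The visit is absent from the percent change and the shift table, and the slope has one point fewer.
5. Under the schedules the count is done anyway, step 1 does not arise, and a sample with no cells is coded None = 0.1.

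**Which samples are at risk.** Protein is itself a trigger. Entry requires PCR above 1 g/g, and the geometric mean of the two samples in the Day -7 to -2 window must still exceed 1 g/g. A subject whose hematuria clears while dipstick protein stays positive still gets microscopy and is coded 0.1. Only samples negative on all four tests are lost.

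**Illustration of leverage.** From the SAP come the codes (16 for 16 - 29 RBCs, None = 0.1, Occ = 0.5) and the geometric mean ratio (GMR). The following are assumed: 15 subjects with baseline hematuria, all at code 16; a 20% fall in those still measured; and k subjects with a fully negative dipstick at the visit.

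With cleared subjects missing, GMR = 0.8, a change of -20% for any k.

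With cleared subjects given code c, GMR = exp{[(15 - k) ln 0.8 + k ln(c/16)] / 15}.

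Here ln 0.8 = -0.223, ln(0.1/16) = -5.075 and ln(0.5/16) = -3.466. On the log scale, one cleared subject coded None weighs about 23 times as much as one with a 20% fall (5.075/0.223).

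| k | Missing | Coded None (0.1) | Coded Occ (0.5) |
|---|---|---|---|
| 1 | -20% | GMR 0.58, -42% | GMR 0.64, -36% |
| 2 | -20% | GMR 0.42, -58% | GMR 0.52, -48% |
| 3 | -20% | GMR 0.30, -70% | GMR 0.42, -58% |

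**Other assumptions.** Take 20 subjects, baseline code 10 to 30, and 1 to 5 cleared and coded None. If the rest are unchanged, 0% becomes -21% (one cleared, baseline 10) to -76% (five cleared, baseline 30). If the rest halve, -50% becomes -59% to -86%.

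The direction is the same throughout. The size depends on the assumed number cleared, the assumed baseline and the code.

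**The case against.** The strongest reply is that the schedules are right. They name the count without condition at every relevant visit, and if sites and the laboratory follow them no value is structurally missing. This stands as a possibility, which is why the point is an inconsistency to reconcile rather than a certain loss. It does not settle the matter, because 7.1.3 is the specific measurement rule. The clause in Protocol 7.10 giving the SAP primacy does not help either: it concerns the analysis methods of that section, and the SAP is silent on an untriggered sample.

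A second reply is that coding a negative dipstick as None is itself an imputation, and at the most favorable value. The documents do not show that a negative dipstick means no cells rather than a few. In an open-label, single-arm study this could replace a bias against the drug with one in its favor. This stands, and it is why the coding route needs a sensitivity analysis.

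Some stronger readings are tempting but not supported:
- *The SAP itself restricts None = 0.1 to samples with microscopy.* It does not. That condition is in Protocol 7.1.3; the SAP only lists the codes.
- *Cleared subjects drop out of the hematuria result.* The loss is per visit. The subject stays in the mITT population, contributes at other visits and can still have a slope. The dipstick result also remains visible in the planned urinalysis shift tables and listing.
- *Every subject whose hematuria clears is lost.* The protein trigger prevents this while dipstick protein is positive. The urinalysis panel in Protocol 7.2.2 does not list protein, but 7.1.3 names it as a trigger, so its absence from the dipstick cannot be inferred. It is worth confirming with the laboratory.
- *The percentages above estimate the bias.* They do not; their inputs are assumed.

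**Conclusion.** The concern holds as a gap between documents with a small, directional consequence. If 7.1.3 governs, a fully negative sample has no RBC value and no rule supplies one. The loss depends on the outcome and works against CCX168. If the schedules govern, the problem disappears, but 7.1.3 then needs correcting.

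Few samples are likely to be affected. Each has high leverage in a geometric mean ratio because of the 0.1 floor: in the assumed example, one cleared subject of 15 moves -20% to between -36% and -42%, depending on the code. The actual size cannot be known from the documents, which give no RBC data, no dipstick thresholds and no laboratory convention for reporting an untriggered sample.

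Hematuria is one of ten other efficacy endpoints. The primary PCR endpoint, the renal response definitions and the sample size are untouched. This is a worthwhile clarification and not a threat to the trial's main conclusion.

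**What to change.** Reconcile Protocol 7.1.3 with the Time and Events Table, the SAP schedule and the visit lists, in one of two ways.

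1. If the schedule governs: state in 7.1.3 that the microscopic RBC count already scheduled is done whatever the dipstick shows.
2. If the trigger governs: add to SAP 10.7.7 that a collected sample with a fully negative dipstick is assigned to None (0.1) and counted in the shift category of 5 or fewer RBCs/hpf; that a sensitivity analysis codes it Occ (0.5); and that only samples not collected or not analysable are missing.

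The second route costs a sentence, a derivation line and one repeat run, with no extra laboratory work. The first adds microscopy only for the few samples that would not have triggered it. The SAP is at version 0.2, so the edit is cheap if made before database lock. The drawback of the second route is that a negative dipstick is only a proxy for a zero count; the Occ analysis shows how much the result depends on that.

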7.1.4. Serum IgA and Plasma C3

Serum samples will be collected for Immunoglobulin A and plasma for complement C3 measurements by specific nephelometry assays by the central laboratory at the study visits indicated in the [Time and Events Table](#).

7.1.5. Plasma and Urinary Pharmacodynamic Markers

Plasma and urine samples will be collected at the study visits indicated in the [Time and Events Table](#). These samples will be stored at -70 °C until measurement. These samples may be used to measure galactose-deficient IgA1, complement factor H, C3a, C5a, properdin, and sC5b-9, cystatin C, other relevant cytokine, chemokine, inflammatory, and other complement markers.

7.2. Safety Assessments

7.2.1. Physical Examinations and Vital Signs

A complete physical examination (including evaluation of general appearance/mental status, HEENT [head, eyes, ears, nose, throat], and the following body systems: dermatologic, cardiovascular, respiratory, gastrointestinal, musculoskeletal and neurologic) for safety assessment will be performed at Screening and Study Days 1, 29, 43, 57, 85, 113, and 169. Physical examination will include a neurological examination including speech, consciousness level, mood, cranial nerves, motor, coordination and gait, reflexes, and sensory systems. Findings must be recorded in the source documents.

Any new or worsening findings upon physical examination need to be recorded as adverse events.

Body weight will be measured at all visits where a physical examination is performed. Body mass index will be calculated based on height, measured at Screening, and each of the body weight assessments.

Vital signs will be measured during Screening and on each scheduled study day as indicated in the [Time and Events Table](#). Blood pressure, pulse rate, and body temperature will be measured. All assessments will be performed while the subject is in the supine position and after the subject has rested for at least three minutes.

7.2.2. Clinical Safety Laboratory Assessments

The following tests will be performed at the visits identified in the [Time and Events Table](#).

- Hematology: hemoglobin, hematocrit, red blood cell (RBC) count, white blood cell (WBC) count with differential, platelet count, mean cell hemoglobin (MCH), mean cell hemoglobin concentration (MCHC), mean corpuscular volume.
- Serum Chemistry: liver panel (bilirubin, lactate dehydrogenase [LDH], SGOT/AST, SGPT/ALT), renal panel (BUN, creatinine), pancreatic enzymes (amylase and lipase), creatine phosphokinase (CPK), albumin, sodium, potassium, magnesium, bicarbonate, chloride, calcium, inorganic phosphorus, glucose, total proteins, alkaline phosphatase, cholesterol, uric acid.

- Urinalysis: At the central laboratory, pH, specific gravity, glucose, nitrite, ketones, bilirubin, urobilinogen, RBC, and WBC tests.
- Virology (measured only at Screening at the local laboratory): hepatitis B surface antigen, hepatitis C antibodies, HIV 1 and 2 antibodies.

7.2.3. Reporting of Adverse Events

An adverse event (AE) is defined as any untoward medical occurrence in a subject participating in a clinical trial who is administered an investigational product, at any dose; the adverse event does not necessarily have to have a causal relationship with this product. An adverse event could therefore be any unfavorable and/or unintended sign (including abnormal laboratory findings), symptom, or disease temporally associated with the use of an investigational product, whether or not considered related to the investigational product. This definition includes intercurrent illnesses or injuries, and exacerbation of pre-existing conditions.

An unexpected adverse event is an adverse event that is not identified in nature, severity, or frequency in the current Clinical Investigator's Brochure, or that is of greater severity than expected based on the information in the Clinical Investigator's Brochure.

All adverse events occurring in subjects who have been enrolled will be recorded on the CRF and will be reported in accordance with regulatory requirements. Adverse events reported prior to commencement of administration of study medication will be considered pre-treatment events.

All adverse events will be monitored until resolution or, if the AE is determined to be chronic, until a cause is identified. If an adverse event remains unresolved at the conclusion of the study, a clinical assessment will be made by the Investigator and the Sponsor's Medical Monitor whether continued follow-up of the adverse event is warranted.

The severity of each adverse event will be determined by the investigator using the following scale:

- Mild (Grade 1): no limitation of usual activities.
- Moderate (Grade 2): some limitation of usual activities.
- Severe (Grade 3): inability to carry out usual activities.
- Life-threatening (Grade 4): an immediate risk of death.
- Death (Grade 5)

The relationship of CCX168 to an adverse event will be determined by the Investigator and Sponsor based on the following definitions:

- Probably Not Related: the adverse event was more likely explained by causes other than CCX168.
- Possibly Related: CCX168 administration and the adverse event occurrence were reasonably related in time, and the AE was explained equally well by causes other than CCX168 or was more likely explained by exposure to CCX168 than by other causes.

A serious adverse event (SAE) is defined as any untoward medical occurrence that at any dose:

- Results in death.

- Is life-threatening (i.e., the patient was, in the opinion of the Investigator, at immediate risk of death from the event as it occurred).
- Requires or prolongs hospitalization.
- Results in persistent or significant disability or incapacity.
- Is a congenital anomaly or birth defect.
- Is an important and significant medical event that, based on appropriate medical judgment, may jeopardize the patient and/or may require medical or surgical intervention to prevent one of the other outcomes defining serious.

Elective surgery, already known during screening to occur in course of the study and elective hospitalizations for convenience of the subject which are clearly unrelated to any medical condition, and agreed between the investigator and the subject prior to randomization, will not have to be reported as SAEs.

A suspected unexpected serious adverse reaction (SUSAR) is defined as an SAE that is considered at least possibly related to study drug (CCX168) and that is unexpected, i.e., not described in terms of nature, severity, or frequency in the current Investigator's Brochure.

Any pregnancies that occur in female subjects or partners of male study subjects must be reported within 24 hours of awareness as indicated in section 7.2.5. All pregnancies must be followed up until conclusion and the outcome of the pregnancy reported within 24 hours of awareness as indicated in section 7.2.5.

7.2.4. Stopping Criteria

Decreases in WBC counts (mostly neutrophil and lymphocyte counts) have been observed in previous clinical trials with CCX168 (see Investigator's Brochure). In an ANCA-associated vasculitis study (CL002_168), subjects have also received cyclophosphamide, which is known to cause leukopenia. Therefore, the contribution of CCX168 to this effect on WBCs is unclear. In this study, CCX168 will not be given cytotoxic compounds such as cyclophosphamide. Therefore, the same extent of decrease in WBC counts is not anticipated. Nevertheless, WBC counts will be monitored regularly over the course of the study. When more than 4 subjects have been enrolled **and dosed with CCX168**, and if more than 25% of these subjects develop **severe leukopenia, neutropenia, or lymphopenia, defined as WBC count < 2000/ μ L, neutrophil count <1000/ μ L, or lymphocyte count <500/ μ L**, deemed possibly related to CCX168 use, the **Sponsor will consider stopping the study. If any subject who receives CCX168 develops severe leukopenia, neutropenia, or lymphopenia, defined as WBC count < 2000/ μ L, neutrophil count <1000/ μ L, or lymphocyte count <500/ μ L, CCX168 use will be interrupted and will not be re-started until the WBC, neutrophil, or lymphocyte count is above the lower limit of normal. If leukopenia/neutropenia/lymphopenia recurs upon re-challenge, CCX168 use will be discontinued permanently in this subject.**

One serious unexpected suspected adverse reaction of elevated liver enzymes has been reported in study CL002_168 in ANCA-associated vasculitis. The study is still blinded as to treatment assignment. The subject also received concomitant cyclophosphamide, pantoprazole, and sulfamethoxazole plus trimethoprim, which all have documented evidence of hepatotoxicity. Nevertheless, hepatic enzymes and bilirubin will be monitored regularly over the course of the

study. **The Sponsor will consider stopping the study if at least one subject develops severe liver injury believed to be caused by CCX168. Severe liver injury is based on Hy's law (elevated aminotransferase of $>3 \times$ upper limit of normal [ULN], alkaline phosphatase $<2 \times$ ULN, and associated with an increase in total bilirubin $\geq 2 \times$ ULN). If any subject who receives CCX168 develops hepatic aminotransferase or total bilirubin elevations of $>3 \times$ ULN, CCX168 use will be stopped in this subject.**

